11.8.2.1 Infusion Premedication and IRR

The analysis in this section will be performed for IRR-2H

Each infusion will be classified based on whether infusion premedication was used for that infusion (Yes/No) and whether infusion premedication was used at baseline (Yes/No) to create 4 categories. This classifies infusions and not patients, so that different infusions for the same subjects can be classified differently for the first question above.

The following will be summarized for each category: the number of post baseline infusions and the number of patients will be presented. The number of post baseline IRR, the number (%) of post baseline infusions with at least one IRR, and the number (%) of patients with at least one IRR. This summary will be for all IRR and for severe IRR.

The analysis will be repeated for infusions in the 1st year of treatment and for infusions in the 2nd year of treatment (including extensions of treatment due to COVID-19).

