14.2 Appendix 2. Infusion Rate Algorithm

[figure not shown]
The infusion rate (IR) may be adjusted according to individual subject symptoms and signs. The infusion rate will be adjusted according to Section 7.5 Study Drug Administration under the direction of the Investigator and Protalix Medical director. Pre-medications will be tapered per Section 7.9 Prior and Concomitant Therapy under the direction of the Investigator and Protalix Medical Director. The assumptions with respect to adverse experiences to the infusion are:

1. Most of the subjects will tolerate the infusion without any special symptom or event.
2. Subjects presenting symptoms and signs of **severe** hypersensitivity will be evaluated according to the CTCAE Drug Toxicity criteria and there may be a discontinuation of treatment according to the protocol.
3. Subjects may present signs and symptoms that will respond to reducing the infusion rate and may not appear at the next infusion.
4. Tolerability and the subject specific infusion rate will be assessed and decided by the Investigator according to vital signs and clinical status of the subject.

Definitions to be applied regarding tolerability of infusions are as follows:

Good tolerability	Partial tolerability	Poor tolerability
Infusion was performed without signs and symptoms (such as burning, pruritus, flushing, discomfort, or change in vital signs).	Signs and symptoms appeared during the infusion and resolved after slowing infusion rate or at the end of the infusion.	Signs and symptoms meeting the definitions of CTCAE Grade 1 or 2 toxicity responding to reduction of infusion rate or responding to treatment (example, antihistamine for urticaria).

The specific algorithm for other infusion rate changes to be followed:

Changes in infusion rates according to the protocol:

The tolerability of the infusions in these patients will be determined by signs and symptoms during the infusion, and observation in the hospital, and by telephone contact the day after the infusion.

For patients with good tolerability after the first 3 months of treatment and the finalization of the attempt of premedication discontinuation (in patients who were previously on premedication) the time of infusion can be decreased by 30 minutes every third infusion, up to a minimum infusion time of 1.5 hours under the agreement between the Investigator and the Medical Director.

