If symptoms resolve within a single study visit and the investigator determines the symptoms were not an occurrence of progressive or severe hypersensitivity, anaphylaxis, or anaphylactoid reactions then administration of the drug may continue according to the algorithm provided above, and at the discretion of the Investigator and Medical Director.

Premedication

Premedication for subsequent PRX-102 infusions may be considered at the discretion of the investigator and Medical Director for subjects experiencing early clinical signs of hypersensitivity or rash/urticaria that responds promptly to oral antihistamine administration (see also Appendix 2 for adjustment of infusion rate). The premedication will be administered according to the following steps as needed to prevent progressive hypersensitivity:

1. Antihistamine (H1 blocker: diphenhydramine, hydroxyzine, cetirizine, loratadine, desloratidine) at a standard dose 12 hours and 2 hours before the start of the infusion.

2. H1 blocker plus H2 blocker (ranitidine, cimetidine, famotidine) at standard doses 12 hours and 2 hours before the start of the infusion.

3. H1 blocker plus H2 blocker plus prednisone up to 50 mg administered 12 hours and 2 hours before the start of the infusion.

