7.2.1 Partial or Missing Dates of Medication

The following imputations will be used in case of incomplete dates of agalsidase-beta treatment required for the calculation of its duration prior to the study:

- The middle of the month (i.e., 15th) will be used if only the day is missing.
- In case the year is not missing, but the month is missing, the month will be imputed to July. If the day is missing as well then it will be imputed to the 1st of July
- No imputation will be done in case the year is missing.

No imputation will be done in case of fully missing medication date.

In some of the analyses, a flag of whether a medication was used at a certain visit is needed (e.g., use of Angiotensin-Converting Enzyme Inhibitor (ACEi) or Angiotensin Receptor Blocker (ARB) treatment at baseline or usage of pain medication at baseline or in the last visit). In case that partial start date and/or end date exist, imputation will be based on the above rules and determination of the flag will be based on the imputed dates and comparison with the date of the visit of interest.

In case that the year is missing from the start date, the determination of usage of a medication at different visits will be based on the stop date of the medication. If the year of the stop date is missing, then the determination will be based on the "Ongoing" status of the medication form as follows: if the ongoing status is Yes then it is assumed that the medication was taken throughout the study (including at baseline and last visits), and if the ongoing status is No then it is assumed the medication was stopped prior to the baseline visit.

Since information on infusion premedication is collected at both the medication form and the drug administration form then determination of usage of infusion premedication at a given visit is based on a different algorithm described in Section 11.8.2.

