11.2.1 Infusion Related Reactions (IRR)

IRRs are those TEAEs which occur during the infusion or shortly after the completion of the infusion and their causality is assessed as definitely, probably, or possibly related.

Injection site reactions with SOC and PT listed in Table 3 are not considered IRR and should not be considered for the IRR analysis.

Two time-frames will be considered for the IRR analysis: during the infusions or within 2 hours after its completion (IRR-2H) or within 24 hours after its completion (IRR-24H). Classification rules for assignment of TEAEs to occur within the time frame are provided below. All IRR tables will be done on IRR-2H. Selected tables will be repeated for IRR-24H, as described below.

Table 3: Injection Site Reaction SOC and PT

MedDRA SOC	MedDRA Preferred Term
General disorders and administration site	Infusion site discomfort
conditions	Injection site discomfort
	Infusion site pain
	Injection site pain
	Infusion site hematoma
	Injection site hematoma
	Injection site extravasation
	Infusion site extravasation
Injury poisoning and procedural complications	Contusion
	Procedural site reaction
	Procedural pain
Vascular disorders	Vein rupture
	Poor venous access

The number and percentage of patients with at least one IRR and the number of IRRs will be reported by treatment group and overall, in an overview table with the following parameters: Any IRR; Mild or moderate IRR; Severe IRR; Serious IRR; IRR leading to withdrawal; IRR leading to death. For selected summary tables, the number of IRR will be shown together with the rate per 100 infusions defined as number of IRR X 100 / Number of Infusions.

This analysis will be repeated for IRR-24H.

This analysis will be repeated for the following sub-groups: ADA status, gender, FD classification and region.

The analysis will be also by the location of administration (Home or Site), and repeated for IRR-24H.

IRR summary tables by SOC and PT will present the number and percentage of patients with at least one IRR and the number of IRRs. The tables for the IRRs will be presented overall, by severity and by seriousness. The tables by SOC and PT will be repeated for IRR-24H.

In summary tables by SOC and PT, SOC will be sorted alphabetically. Within SOC, PT will be sorted in a decreasing order of PRX-102 frequency.

IRR-2H and IRR-24H will be listed.

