11.8.2 Infusion Premedication

Information on infusion premedication is collected on two different forms in the eCRF: in the concomitant medication eCRF form where the identification of medications used for that purpose is done by the classification provided by investigator. In addition, the drug administration form, collects information whether premedication was used or not in relation to each infusion (and if yes, the timing – before, during or before and during infusion).

Infusion premedication will be tabulated by treatment arm by medication class and standardized medication name. Medication classes will be presented alphabetically; within each medication class, standardized names will be sorted by decreasing order of PRX-102 frequency.

A summary table of the number (%) of patients with and without premedication use at each visit by treatment group will be derived based on the drug administration form.

A shift table, to identify how many patients changed the number of infusion premedication from baseline to Week 52 and Week 104 (or the last assessment before discontinuation) will be presented. The shift table will include the following categories: 0, 1, 2, 3+. In order to assess for each subject if any infusion premedication was used at baseline or at Week 52 or 104 or last assessment, the drug administration form at that visit will be used. If based on this form, no premedication was administered then the number of infusion premedication at that visit is 0. In case premedication administration at visit of interest is confirmed from drug administration form, the number of infusion premedication for each subject will be determined by the number of medications reported in the concomitant medications form in the eCRF, in which classification for infusion premedication is marked, and the date of the study drug infusion is within the start and end date of the premedication. Note that physician may change instructions for medication several days before the visit, so no window should be considered when comparing the dates. In case of missing or partially missing dates of infusion premedication, the following imputation rules should be considered before comparing the study drug infusion date to the medication start/end dates:

- When the start date is completely missing or the year is missing then it's assumed the medication was taken at baseline.

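### The premedication-by-IRR table ignores the recorded timing, so a drug given during an infusion to treat a reaction could put that infusion in the premedicated category

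*SAP*

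**What the plan says.** SAP 11.8.2.1 crosses two binary flags to form four categories of infusion. One flag is premedication at baseline; the other is premedication at the infusion itself: "Each infusion will be classified based on whether infusion premedication was used for that infusion (Yes/No". For each category it reports the number and percentage of post-baseline infusions with at least one IRR. This is done for all IRRs and for severe IRRs, and repeated by year of treatment. The outcome is fixed: "The analysis in this section will be performed for IRR-2H". SAP 11.2.1 defines that window as "during the infusions or within 2 hours after its completion (IRR-2H".

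Section 11.8.2.1 names no source form. SAP 7.2.1 says that "determination of usage of infusion premedication at a given visit is based on a different algorithm described in Section 11.8.2". Section 11.8.2 in turn describes a drug administration form that records, for each infusion, whether premedication was used, "and if yes, the timing – before, during or before and during infusion". The by-visit counts of patients "with and without premedication use at each visit by treatment group will be derived based on the drug administration form". Neither section uses the timing answer to decide what counts as Yes.

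On the clinical side, Protocol Appendix 3 times one set of premedication steps before the infusion: "at a standard dose 12 hours and 2 hours before the start of the infusion". Protocol Appendix 2, in defining poor tolerability, mentions signs and symptoms "responding to treatment (example, antihistamine for urticaria".

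**The concern.** The table relates an exposure (premedication) to an outcome (a reaction during or shortly after the same infusion). Exposure should therefore be settled before the outcome can occur. With *during* accepted as a form of Yes, it need not be. Suppose an infusion starts without premedication, a reaction occurs, an antihistamine is given, and the site ticks premedication with timing *during*. That infusion moves from the unpremedicated to the premedicated category and takes its reaction with it.

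The analysis was added to the final SAP following the Summary of Clinical Safety for the MAA (SAP 13.2, item 16). The ability to taper premedication and the need for it are protocol safety variables (Protocol 8.3). Readers will look to this table to judge how infusions without premedication fare.

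**Working it through.** The plan states no figure for this table, so there is none to reproduce. The check has two parts.

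**1. The rule as written**

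- The flag is Yes/No with no timing condition (SAP 11.8.2.1).
- The form's Yes covers *before*, *during*, and *before and during* (SAP 11.8.2).
- IRR-2H includes onset during the infusion (SAP 11.2.1).
- Nothing in either document requires the drug to precede the reaction.

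The error runs one way. An infusion with a dose before the start is Yes whether or not a reaction is later treated. Only an infusion with no dose before the start can change category. When the reason is reaction treatment, it arrives in the premedicated category with an IRR by construction. Reactions that begin after the infusion ends cannot be treated during it, so the mechanism is limited to IRRs with onset during the infusion.

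**2. Illustration of size (all inputs assumed)**

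Let *p* be the share of infusions truly premedicated before the start. Let *r* be the share of infusions with an IRR, set equal in both groups so that there is no true effect. Let *f* be the share of unpremedicated infusions with an IRR that are recorded as *during*.

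- Apparent rate, Yes = [p·r + f·(1−p)·r] / [p + f·(1−p)·r]
- Apparent rate, No = [(1−f)·(1−p)·r] / [(1−p) − f·(1−p)·r]

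With p = 20% and r = 1%, per 1,000 infusions:

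| f | Yes | No | Ratio |
|---|---|---|---|
| 0% | 2.0/200.0 = 1.00% | 8.0/800.0 = 1.00% | 1.0 |
| 10% | 2.8/200.8 = 1.39% | 7.2/799.2 = 0.90% | 1.5 |
| 25% | 4.0/202.0 = 1.98% | 6.0/798.0 = 0.75% | 2.6 |
| 50% | 6.0/204.0 = 2.94% | 4.0/796.0 = 0.50% | 5.9 |

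The result depends strongly on *p* and hardly at all on *r*:

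- At r = 1% and f = 10%, the ratio is 3.2 for p = 5% and 1.3 for p = 40%.
- At r = 1% and f = 25%, it is 7.3 for p = 5% and 1.8 for p = 40%.
- At p = 20%, raising r to 5% changes the ratios for f = 10% and f = 25% only to 1.5 and 2.5.

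The distortion is therefore largest where few infusions are truly premedicated. The baseline-No/infusion-Yes cell is the likeliest place. The severe-IRR version is also exposed, because severe reactions are the ones most likely to be treated.

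**The case against.** The strongest reply is that the key step is not documented. No text says that sites enter reaction treatment under the premedication question, and the form's completion instructions are not in the documents. Several places suggest separate recording. The adverse event description includes whether treatment was required (Protocol 8.3.2.2). Investigators classify which concomitant medications are infusion premedication (SAP 11.8.2). Appendix 3 puts reaction treatment and premedication under different headings. It also says to stop the infusion at the onset of the listed signs, so later treatment may not be recorded as *during* at all. The Appendix 2 antihistamine example does not say when the drug is given. All of this stands, and it means the size of any bias is unknown and could be nil. It does not rule the mechanism out: Protocol 7.9 and 8.3 themselves speak of premedication used to manage infusion reactions.

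A reader might infer that the protocol defines premedication as drug given before the infusion, so that every *during only* entry is misclassified. The documents do not support that. The Appendix 3 schedule applies to premedication newly considered after early signs of hypersensitivity, or after rash or urticaria that responds promptly to an oral antihistamine. Premedication carried over from agalsidase beta has no stated timing (Protocol 7.9 and Appendix 8). A *during* entry could be planned prophylaxis.

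A reader might also infer that the shift table in SAP 11.8.2 overstates continued use to the same degree. It is partly protected. After a Yes on the form, it counts only concomitant medications that the investigator classed as infusion premedication and whose dates span the infusion.

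Finally, the table has no test or decision rule. It is already confounded, because premedication is resumed in patients who react (Protocol Appendix 8). Listing 16.2.3.7.2 shows premedication and IRR-2H by visit. These points limit what is at stake. They do not excuse an avoidable second problem: confounding by patient history is unavoidable here, whereas defining exposure by the outcome can be removed with a field already on the form.

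**Conclusion.** The gap in the rule is established from the text, on the inference that the drug administration form is the source. A plain Yes/No that includes drug given only during the infusion lets the premedication category be set after, and because of, the reaction it is compared with. Such entries can only make premedicated infusions look more reactive and unpremedicated ones less so.

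That this has happened is not established. The ratios of 1.0, about 1.5 and 2.6 rest wholly on the assumed 20% premedicated, 1% IRR rate and 0%, 10% and 25% recorded as *during*. The documents give none of these. The claim that the table, as written, does make premedicated infusions look worse would go too far; it can do so.

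The consequence is confined to a descriptive safety table. The by-visit premedication counts use the same form and can be affected only to the extent that reactions were treated and recorded this way. The shift table is a minor point. The primary endpoint is unaffected. The change should still be made, because it is nearly free and changes nothing if no *during only* entries exist.

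**What to change.** In SAP 11.8.2.1, and for the by-visit table in 11.8.2:

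- State that the drug administration form is the source.
- Count an infusion as premedicated only if the recorded timing is *before* or *before and during*.
- Show *during only* infusions as a separate category with their IRRs. Do not fold them into either group, because the documents do not settle whether they are prophylaxis or treatment.

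With two baseline groups, the IRR table then has six categories instead of four. If the baseline flag comes from the same form, apply the same condition to it.

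The cost is a sentence or two in the SAP, one condition in the program and one extra category in each table. No new data are needed. A pooled count of *during only* entries, made by the blinded team before database lock, would show at once whether the issue matters in practice.

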11.9 Brain MRI

Brain MRI will be listed.

11.10 X-Ray

X-ray will be listed.

12. ANALYSIS OF PK ENDPOINTS

PK analysis, derivation of parameters and PK summary statistics will be described in a separate Pharmacokinetic Analysis Plan.

13. CHANGES IN PLANNED ANALYSIS

13.1 Changes from Protocol to Interim Analysis SAP

The statistical section of the protocol is short and was not meant to provide detailed information for the analysis. Some of the changes in the planned analysis of PB-102-F20 are due to knowledge and insights gained in the overall clinical program of PRX-102. The analysis of the primary endpoint and its associated sensitivity analyses were discussed and agreed by the FDA. The main changes in the analysis plan compared to protocol are as follows:

- 1. The following endpoints were added: Infusion Related Reaction (IRR), Fabry Clinical Events and Achievement of Fabry Kidney Disease Therapeutic Goals.
- 2. Analysis sets: the protocol defined that a patient who received at least one complete dose will be included in the ITT and the SAP changed this to also include at least one partial dose. The definition of the Per Protocol population was also slightly revised.
- 3. The primary analysis was discussed with the FDA after protocol was finalized, and the agreement is described in the SAP. In particular added clarity on the choice of mixed model used, method of estimation and covariance matrix. UPCR which is a stratification factor was added as a covariate which is in line with ICH-E9. The discussion with the FDA included sensitivity for missing data and for modeling assumptions, which is different from what was described in the protocol.
- 4. The protocol specified assessment of the linearity assumption via residual plots. This was changed and instead it will be assessed by the MMRM model on the change in eGFR which does not assume linearity. In case of disagreement, additional assessments will be performed post-hoc.
- 5. The approach for multiplicity control was changed from the protocol, and was discussed and agreed with the FDA.
- 6. The only shift table for laboratory value will be for ADA. No other shift tables will be performed as no other safety laboratory values are of special interest.
- 7. Evaluation of Acute Kidney Injury is based on AE reporting and clinical judgment of the investigator and not as described in the protocol.
- 8. The statistical section of the protocol stated that hypersensitivity will be analyzed as an AE of special interest. Since IRR is a wider analysis which was added (see item 1 in this list), the analysis of hypersensitivity will be part of the IRR evaluation.

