10.4.2 Clinical Laboratory

Clinical Laboratory examination will be performed prior to treatment and during treatment.

Descriptive statistics will be presented for the value and abnormality of each of the clinical laboratory results by visit and dose group. Shift tables describing abnormality shifts from baseline to after treatment and follow-up will be created.

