11.5 Clinical Laboratory Test Results

The following laboratory test results will be summarized by treatment arm at each visit. Continuous measures will include the change from Baseline:

- 1. Hematology: Hemoglobin (g/dL), Platelets (/mm3), Total white blood cell count (/uL)
- 2. Coagulation Profile: Partial thromboplastin time (PTT; sec), Prothrombin time (PrT; sec)
- 3. Vitamin D: D2 (pg/mL), D3 (pg/mL), 1,25-Dihydroxyvitamin D (pg/mL)
- 4. Urinalysis: Dipstick for presence of blood, Dipstick for presence of glucose, Dipstick for presence of Protein.
- 5. Biochemistry: Alanine transaminase (U/L), Albumin (g/dL), Alkaline phosphatase (U/L), Aspartate transaminase (U/L), Bilirubin (total) (mg/dL), Blood urea nitrogen (mg/dL), Calcium (mg/dL), Creatinine (mg/dL), Creatine phosphokinase (U/L), Cystatin c (mg/L), Gammaglutamyl transferase (U/L), Glucose (mg/dL), Lactate dehydrogenase (U/L), Phosphate (inorganic) (mg/dL), Potassium (mEq/L), Sodium (mEq/L), Total protein (g/dL) and Uric acid (mg/dL).

Note: serum creatinine can be recorded in two units, μ mol/L and mg/dL. In calculation of eGFR or summary of creatinine, the value in μ mol/L needs to be converted to mg/dL using the following conversion formula: 1 mg/dL = (1/88.4) μ mol/L.

Note: Serum creatinine is present in two laboratory test categories in the Study Data Tabulation Model (SDTM) (CHEMISTRY and ENZYMATE). When results from the same sample are entered at both laboratory test category, then the value is identical. In such cases, only one of them will be used in the analysis.

In case that blood sample is taken twice at the same visit, only the results of the first blood sample (based on the time the blood sample was taken) will be used in the analyses, but both will be listed.

All collected laboratory results will be listed (also parameters that are not tabulated).

Descriptive statistics for parameters for which there are test results below the level of detection and reported as '<', will not include the change from baseline analysis. For these parameters, the analysis of actual values at the visit will be based only on the values for which the true value was observed, and the summary will indicate the number of observations that were below the limit of detection. In the listings, these observations will be presented with the '<' sign.

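### The SAP drops the protocol's laboratory abnormality shift tables and, without declaring it, its abnormality summaries; for parameters with results below the detection limit it uses detected values only and omits change from baseline.

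*SAP*

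**What the plan says.** Protocol 10.4.2 (Clinical Laboratory) makes two commitments. The first is by-visit description: "Descriptive statistics will be presented for the value and abnormality of each of the clinical laboratory results by visit and dose group". The second is shift tables: "Shift tables describing abnormality shifts from baseline to after treatment and follow-up will be created". The Safety Endpoints list in the protocol synopsis puts clinical laboratory tests under changes from baseline.

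SAP 13.1 item 6 withdraws the second commitment: "The only shift table for laboratory value will be for ADA". Its reason is "No other shift tables will be performed as no other safety laboratory values are of special interest".

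SAP 11.5 opens its laboratory plan with "The following laboratory test results will be summarized by treatment arm at each visit", adding change from baseline for continuous measures. It mentions no classification against reference ranges. The table list in SAP 14.1 has five laboratory safety tables (14.3.6.1 to 14.3.6.5), all titled as summaries. Neither 13.1 nor 13.2 lists removal of the abnormality summary as a change.

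For parameters with results reported as `<`, SAP 11.5 says that the descriptive statistics "will not include the change from baseline analysis" and that the analysis of values at each visit "will be based only on the values for which the true value was observed". The count of `<` results is shown in the summary, and every result is listed with its sign.

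SAP 7.1 confines by-visit summaries to scheduled visits, unless otherwise specified. Unscheduled procedures and premature-withdrawal data are listed, not tabulated.

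**The concern.** The reason given for dropping the shift tables assumes the answer. A shift table is a routine screen for laboratory changes that nobody expected, so the absence of a parameter of prior interest is no argument against it. The SAP keeps normal/abnormal counts for physical examination (11.4) and counts of abnormal findings for ECG (11.6). Haematology and biochemistry therefore get a weaker summary than either.

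At stake is a simple between-arm comparison: how many of about 52 and 26 patients left the reference range on treatment, counted the same way for everyone and independently of the investigator's view of clinical significance.

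The rule for `<` results raises a second problem. Removing the lowest values raises the mean. If the undetected share differs between arms or visits, the distortion differs too, and the change-from-baseline rows that might expose it are removed for the whole parameter.

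**Working it through.** The plan states no figure on this point, so there is none to reproduce. The check has two parts.

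**1. What each planned output can show**

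- *By-visit summaries (SAP 7.1, 11.5).* These give n, mean, SE, SD, median, minimum and maximum. A gross value at a scheduled visit would appear as the maximum. The table would not show how many patients crossed a limit, or whether they were already outside it at baseline.
- *Visit means.* As an illustration, let 3 of 52 patients rise by 3 SD. The arm mean moves 3 × 3/52 = 0.17 SD, against a standard error of 1/√52 = 0.14 SD. The mean is a weak detector, and the maximum reveals one of the three.
- *Unscheduled, repeat and withdrawal samples.* SAP 7.1 lists unscheduled and withdrawal results only. Where two samples are taken at one visit, SAP 11.5 analyses the first. Later confirmatory values therefore enter no laboratory summary.
- *Adverse events.* Protocol 8.3.2.1 requires an abnormality to be recorded as an AE if the investigator judges it clinically significant, and SAP 11.2 counts patients with TEAEs by arm. This count depends on that judgment.
- *Other counts.* Dipstick results are categorical and get counts by visit. UPCR has a category shift table (14.2.9.2). SAP 9.5 counts patients with a 1.5-fold creatinine rise over the previous value. None of these classifies haematology or biochemistry against a reference range.
- *Screening-only tests.* Coagulation and vitamin D are scheduled at screening only, so the loss mainly concerns haematology and biochemistry.

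**2. Effect of using detected values only**

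Let p be the share below the detection limit and z the standard normal quantile at p. Normality and p are assumptions; the documents give neither.

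Upward bias of the detected-only mean, in SD units, is φ(z)/(1 − p):

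- p = 10%: 0.1755/0.90 = 0.195
- p = 20%: 0.2800/0.80 = 0.350
- p = 30%: 0.3477/0.70 = 0.497

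The detected-only median is also displaced, whatever the distribution. It sits at overall percentile p + (1 − p)/2, which is 0.10 + 0.45 = 55% at p = 10% and 0.30 + 0.35 = 65% at p = 30%.

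A real fall is understated when visit means are compared. Take 10% undetected at baseline (z = −1.2816) and a true fall of 0.5 SD with the same limit. The undetected share becomes Φ(−0.7816) = 0.217, and the detected mean becomes −0.5 + 0.294/0.783 = −0.125. The apparent fall is 0.195 + 0.125 = 0.32 SD instead of 0.5.

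For comparison, setting `<` results to the detection limit leaves an upward bias of φ(z) + z·p:

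- p = 10%: 0.1755 − 0.1282 = 0.047 SD
- p = 30%: 0.3477 − 0.1573 = 0.190 SD

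This is smaller, but not zero.

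**The case against.** Removal of the shift tables is itemised with a reason, and SAP Section 1 says that the SAP governs where it differs from the protocol. That part is therefore not a hidden contradiction. Precedence settles which text applies; it does not supply the missing counts. It also does not cover the abnormality summary, whose removal is not declared.

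A reader might go further and infer that a marked abnormality would surface only in a listing or as an AE. The documents do not support that, because SAP 7.1 requires minimum and maximum and a scheduled-visit extreme would be visible. Nor can one say that no table at all counts patients with abnormal laboratory findings: clinically significant abnormalities are counted as TEAEs, and dipstick and UPCR results are counted by category. The gap is the count against reference ranges for haematology and biochemistry.

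A reader might also infer that the trial's laboratory means are biased upward. No safety parameter is identified as having `<` results, and no share is given. The only stated detection limit, for urine protein, is in SAP 10.6, where UPCR observations are kept and the sign is ignored. Showing the number of `<` results also lets a careful reader see the missing share by arm and visit. That discloses the problem but does not correct the statistics or restore change from baseline.

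Finally, the table shells (SAP Section 15) are not available here, so an abnormality column in them cannot be excluded.

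**Conclusion.** The point holds in a limited form. As written, the SAP provides no haematology or biochemistry table showing how many patients per arm moved outside the reference range, although the protocol promised both abnormality summaries and shift tables. One removal is declared on weak grounds; the other is not declared. The remaining outputs cover the gap only in part.

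The bias from the `<` rule is certain in direction for any affected parameter but conditional on there being one. Under normality it is about 0.2 SD at 10% undetected and 0.5 SD at 30%. The true share is unknown and may be negligible. Loss of change from baseline for an affected parameter follows directly from SAP 11.5 and cuts into a protocol safety endpoint.

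This is a weakness in safety reporting. It does not touch the primary efficacy analysis. It is worth correcting because the remedy is cheap.

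**What to change.** In SAP 11.5, 13.1 and 14.1:

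1. Restore abnormality shift tables by arm for haematology and biochemistry. Protocol 10.4.2 fixes no format. One suitable choice is baseline to worst post-baseline value, including unscheduled and withdrawal visits, plus baseline to Week 104.
2. Add, by arm, the number and percentage of patients with any post-baseline value outside the reference range.
3. For parameters with `<` results, keep all patients. Report median and quartiles with `<` ranked lowest. Compute change from baseline with `<` set to the detection limit, and state that this is an approximation. Continue to show the number of `<` results.
4. If any part of the protocol's abnormality summary is still to be omitted, list that as a change and give the reason.

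The cost is a few more safety tables, using standard programming on results already collected. This assumes that the laboratory's reference ranges are held with the results, which the documents do not state for each parameter.
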